3.4 Secondary Outcome Measure(s)

The secondary outcome measure is response to the question “I achieved my specific objectives for the rotation (which the learner provided at the start of the rotation).” It will be quantified using a Likert scale with five choices, 1-5, with 1 set to strongly disagree and 5 set to strongly agree.

Other outcome measures include whether (via Likert scale, scores ranging from Strongly Disagree to Strongly Agree as defined above):

- The learner was provided with a variety of resources to meet their learning objectives
- The education they received matched their level of training
- Their education was appropriate to their previous exposure to hospice and palliative medicine
- The education matched their learning style
- They felt the rotation was valuable

- The clinical educators promoted an open, respectful, and safe environment for discussion, learning, and improvement
- They would recommend this rotation to others

Open-ended feedback will be elicited regarding strengths of the rotation, areas for improvement, and practice changes, both on the survey and during the focus group.

Lastly, learners will be assessed on their confidence in meeting each standard rotation objective, on a Likert scale of 1-5, both before and after the rotation.

All of this allows the team to gather more information to understand why there was benefit for the flexible learning curriculum, if indeed there was one.

Section 4: Study Design

This is a single-center pilot study evaluating the use of a flexible curriculum tool to improve the experience of rotators with the palliative care team, measured by how well the rotation helps them meet standard as well as individualized learning objectives. It will not be blinded.

All learners will be sent a welcome email that will include a pre-rotation self-assessment, identifying type of learner and personal experience with palliative care, self-identified preferred ways of learning, length of time on the rotation, and personal learning goals.

All learners in the first half of the study period will be in the control group, and all learners in the second half of the study period will be in the intervention group. Outcomes will be measured on post-rotation evaluation surveys, one for each trainee, sent to them after their rotation is complete. Qualitative data will be more deeply interrogated with a focus group of trainees who participated in the intervention.

Section 5: Study Enrollment and Withdrawal

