6.3 Study Interventions and Follow-Up

Database Development. Initial database development will be done in Microsoft Excel until June 2026. This database will include links to a variety of resources in the following categories, to be used alongside experiential and on-the-fly teaching: didactics (lectures by palliative care faculty, seminars from other sources, online lectures, videos, and podcasts), interactive resources (online modules, interactive websites, simulations), and written resources (books, articles, handouts, and websites or blogs). Topics covered will include palliative care symptom management, communication in different circumstances, diagnostic, prognostic and treatment information, decision making, ethics, active resources for patients and families, hospice, psychosocial and spiritual support of patients and families, end of life care, and well-being and self-care.

Every resource will be characterized based on questions answered in a learning self-assessment, when a trainee begins their rotation. It will ask about standard objectives and elective objectives, level of training, experience in hospice and palliative medicine, learning style, and time on service. Starting in July 2026, for each trainee in the intervention group, a curriculum will be built per their rotation specifications. Following the tailored curriculum, learners will be given an evaluation to evaluate how effective the rotation experience was at meeting the objectives.

Intervention Implementation. Between January – June 2026, the rotation education will continue as normal for the control group. Rotators will be sent an

introductory email with standard rotation goals and learning objectives and resources. They will share their individual learning objectives on the first day of the rotation. Preceptors will provide resources and clinical opportunities in an *ad hoc* manner for learning based on their individual learning objectives, as is the standard right now. Between July – December 2026, learners with the team will be asked to provide answers to the self-assessment approximately one month before the start of the rotation, and the flexible curriculum tool will be used to generate a tailored set of resources for them. Of note, some rotators organize their rotation on a shorter time frame, and for those learners, the self-assessment will be sent when they set up their rotation to be done as soon as possible.

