8.2 Statistical Hypotheses

Primary Outcome Measure:

- Hypotheses:

- Null: There is no difference (in terms of central tendency) between the two groups in their response (using a Likert scale) to the question, “I achieved the standard objectives of the rotation.”
- Alternative: There IS a difference (in terms of central tendency) between the two groups in their response (using a Likert scale) to the question, “I achieved the standard objectives of the rotation.”

Secondary Outcome Measures:

- Hypotheses:
 - Null: There is no difference (in terms of central tendency) between the two groups in their response (using a Likert scale) to the question, “I achieved my specific objectives for the rotation.”
 - Alternative: There IS a difference (in terms of central tendency) between the two groups in their response (using a Likert scale) to the question, “I achieved my specific objectives for the rotation.”

For the remaining secondary outcome measures evaluated using a Likert Scale, the hypotheses will be like those of the above measures, as they are all evaluated using Likert scales.

For the secondary outcome measures evaluating using Likert Scales at pre- and post-participation time points, the hypothesis is as follows:

- Hypotheses:
 - Null: There is no difference in mean between the two groups in the degree of change between pre- and post-intervention confidence (for each individual objective)
 - Alternative: There IS a difference in mean between the two groups in the degree of change between pre- and post-intervention confidence (for each individual objective)

There are no hypotheses for the analysis of the open-ended survey questions and focus group data, as they will be analyzed using inductive thematic analysis.^{12,13}

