8.4 Description of Statistical Methods

This study is a pre-/post-interventional study; however, different participants will receive the intervention than those that receive the control education because of the nature of the palliative care rotation. Essentially, for the first 6 months of the study period, rotators will receive the control education, and for the next 6

months of the study period, they will receive education using the intervention, the flexible education tool. All evaluations from each 6-month period will be aggregated to preserve anonymity, and there will be no learners who are in both groups.

Demographic data will be collected during the self-assessment and reported using descriptive statistics:

- Level of training (categorically in percentages)
- Amount of experience in hospice and palliative medicine (categorically in percentage)
- Learning style (categorically in percentages)
- Time on palliative care service (categorically in percentages)

For all outcome measures that use Likert scales (ordinal data), the sample size is so small that it is assumed data will not fall within a normal distribution, so a Mann-Whitney U test will be to analyze it and report z-test statistic and p-value, as well as the interquartile range. A p-value of 0.05 will be used for statistical significance.

Individual participant data will not be published.

Confidence ratings will be compared at pre-post time points for significant improvements within each group using a paired t-test. Overall improvement between control and intervention groups will be compared using a student's t-test to compare the change in confidence. A p-value of 0.05 will be used for statistical significance.

Qualitative data, including responses to open-ended survey questions and focus group data, as mentioned in 8.2, will be analyzed using inductive thematic analysis using DeDoose software.

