8.6 Measures to Minimize Bias

Enrollment/Randomization/Masking Procedures

- There will be no randomization, as it is a convenience sample based on when learners have room in their schedule to rotate with the palliative care team

- Based on the way the intervention will be implemented, it is impossible to blind the educators or the rotators as to whether the rotators are in the control or intervention group
- The control and intervention survey data will not be analyzed until after all data is compiled (control data in August 2026 and intervention data in February 2027), and data will have all identifying information (timestamps, etc.) removed.
- Bias will be minimized in the qualitative data using triangulation – independent analysis by multiple personnel as well as comparison of open-ended survey data with focus group data

Section 9: Data Quality and Oversight

Survey data will be de-identified and collected via REDCap. It will be stored in their database until completion and publication of the study. It will be accessible only to authorized users via password. Data downloaded for analysis in an Excel file will have data and timestamps removed.

Focus group data will be de-identified when it is transcribed. It will be conducted over teleconference software (Teams) but recorded via audio recorders outside of the Teams software, so as to not capture visual data. Additionally, participant names will not be used, and they will be referred to as “participant 1”, “participant 2”, etc. Recording will be transcribed using Rev AI transcription software. Recordings and transcriptions will be stored on a password protected shared drive.

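### The confidence comparison relies only on an unadjusted change score between non-randomized cohorts, so a lower starting level could pass for a tool effect; a baseline-adjusted estimate should stand beside it

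*Protocol*

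**What the plan says.** Section 3.4 has learners rate their confidence in each standard objective "on a Likert scale of 1-5, both before and after the rotation". Section 8.4 states "Overall improvement between control and intervention groups will be compared" "using a student's t-test to compare the change in confidence", and adds "A p-value of 0.05 will be used for statistical significance". The null hypothesis in Section 8.2 matches that test: "There is no difference in mean between the two groups in the degree of change between pre- and post-intervention confidence", for each objective.

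On allocation, Section 8.6 says "There will be no randomization, as it is a convenience sample based on when learners have room in their schedule". Section 6.3 sets the periods: "Between January – June 2026, the rotation education will continue as normal for the control group", and the tool is used from July to December 2026. Section 8.4 confirms that the two groups are different people. Level of training, palliative care experience and time on service are collected, but only for description. The bias measures in Section 8.6 do not deal with unequal starting levels. Section 8.1 says there will be no separate SAP, so 8.4 is the whole plan for this comparison.

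**The concern.** The pre-rotation rating enters the between-group comparison only by subtraction. On a scale that stops at 5, a learner who starts at 2 has three points to gain and one who starts at 4 has one. If low starters tend to rise more, the cohort with the lower starting level shows the larger mean change whether or not the tool works.

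Unequal starting levels are realistic. Section 2.2 describes learners of various levels and experience, with half a day to a few months on service, and Section 8.5 expects only 10 to 15 per group, so chance alone can produce a gap. If the academic year begins in July (an assumption), controls rotate late in one year and intervention learners early in the next. That would tend to put the less experienced learners in the intervention group. What is at stake is a confidence result that Section 3.4 intends to help explain any benefit of the tool.

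**Working it through.** The protocol states no effect size, standard deviation or power for this outcome, so there is no planned figure to reproduce.

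**Inputs from the protocol:** 10 to 15 per group (8.5); 1–5 scale (3.4); significance level 0.05 (8.4), taken as two-sided because 8.2 states a non-directional alternative.

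**Assumed, not in the protocol:** intervention cohort starts 0.5 or 1.0 point lower; true tool effect zero.

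**Step 1: how the two estimates relate.** Let *g* be the amount by which the intervention cohort starts lower, and *b* the within-group slope of post on pre.

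- Change estimate = (difference in post) + *g*
- Adjusted estimate = (difference in post) + *b* × *g*
- Change minus adjusted = (1 − *b*) × *g*

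The two coincide when *g* = 0 or *b* = 1. Otherwise:

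| Slope *b* | *g* = 0.5 | *g* = 1.0 |
|---|---|---|
| 0 (all converge on a common end level) | 0.50 | 1.00 |
| 0.5 (each closes half the distance to 5) | 0.25 | 0.50 |
| 1 (all gain the same amount) | 0 | 0 |

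**Step 2: false positives of the change test, hand check.** At 10 per group the noncentrality is (spurious gain) / (SD of change × √(2/10)), on 18 degrees of freedom.

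- Half-distance model, assumed SD of change 0.8: 0.25 / 0.358 = 0.70, rejection about 10%; 0.50 / 0.358 = 1.40, about 26%.
- Common-end model, assumed SD of change 1.0: 0.50 / 0.447 = 1.12, about 18%; 1.00 / 0.447 = 2.24, about 56%.

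**Step 3: simulation with ratings rounded and bounded to 1–5.** Assumed control mean 3.5, latent SD 0.8, rating error SD 0.4, no tool effect. Change-test entries are rejection rates for gaps of 0.5 / 1.0.

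| How learners improve | Change test, 10 per group | Change test, 15 per group | Adjusted test |
|---|---|---|---|
| Common end level | 15% / 44% | 22% / 60% | 5–6% |
| Half the distance to 5 | 11% / 23% | 13% / 38% | 6–8% |
| Equal gain, capped at 5 | 6–9% | 6–9% | 7–15% |

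With equal starting levels the change test rejects in 4–5%. Other runs of the capped model gave 8–23% for the 1.0-point gap over the two group sizes. Across the models and spreads tried, the range at 10 per group is about 6–20% for a 0.5-point gap and 9–61% for 1.0.

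**Step 4: the opposite case.** Suppose group differences are stable over time, so both cohorts truly gain the same amount. The change test then rejects in 5–6%. The adjusted test rejects in about 7–42% over gaps of 0.5 to 1.0, pre–post correlations of 0.3 to 0.7 and 10 to 15 per group. The direction follows from Step 1: with no tool effect and a fitted slope of 0.5, the adjusted estimate is −(1 − 0.5) × *g*, that is −0.25 or −0.50, against a lower-starting intervention cohort.

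**The case against.** The strongest reply is that nothing here is misstated. Section 8.2 asks about a difference in mean change and the t-test in 8.4 tests exactly that. In non-randomized groups, the choice between change scores and baseline adjustment has no general answer (Lord's paradox), and Step 4 shows adjustment failing where the change score holds. This is also the last-listed outcome of a pilot whose Section 8.5 accepts that it may be underpowered, and adjusting for one rating does not make two calendar cohorts comparable. All of that stands. It rules out calling the planned test wrong or replacing it. It does not answer the narrower point: the plan shows only one of two estimates that can disagree, and gives the reader no starting levels from which to see it.

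A reader might go further and infer three things the documents do not support.

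- *The result will be biased towards the tool.* No baseline ratings are given, so the size and direction of any gap are unknown; a higher-starting intervention cohort would reverse the sign.
- *Adjustment is the correct analysis.* Its rejection rate stays near 5% only under some models.
- *Benefit should be claimed only if both tests are significant, with adjustment repaying the lost power.* For an assumed 0.8-point effect, equal baselines and 12 per group, simulated power is 28–47% for the change test alone, 43–58% for the adjusted test alone and 23–42% if both must be significant. That rule leaves less power than the present plan.

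**Conclusion.** The point holds as a modest improvement. Section 8.4 relies on a single unadjusted change score, on a bounded scale, between cohorts that may start at different levels. With no tool effect, the nominal 5% could become about 6–20% (0.5-point gap) or 9–61% (1.0-point gap) at 10 per group. This requires that the intervention cohort starts lower and that low starters rise more; both are assumptions. If differences between the cohorts are stable, the planned test is sound and the adjusted one errs. The protocol contains nothing that decides between these cases, which is the reason to show both estimates. The primary outcome is not affected.

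**What to change.** In Section 8.4:

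1. Report pre-rotation confidence by group for each objective.
2. Keep the change-score t-test, and add beside it a comparison of post-rotation confidence adjusted for the pre-rotation rating. Give both estimates with 95% confidence intervals.
3. State that if the two estimates differ materially, the confidence result will be reported as sensitive to baseline imbalance and not as evidence of a tool effect. Do not require both tests to be significant.

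The cost is one extra regression per objective on ratings already planned, and a more cautious conclusion when the estimates disagree. Adjustment does not remove other differences between the cohorts. It needs each learner's pre and post ratings linked, as the paired t-test and the change score in 8.4 already do. Section 6.1 says nothing will tie identity to responses, while Section 10.4 refers to a unique study number, so the protocol should say how the link is made.

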8.5 Sample Size

Because this is a pilot study to improve the education of an existing population on a rotation with a small team, the sample will be a convenience sample of learners who rotate with the palliative care team. It is expected that there will be approximately 20 learners to recruit and screen for each (control and intervention) group and to enroll at least 10 and up to 15 for each group. It is accepted that the statistical analysis may be underpowered, which is why the pilot study will be supplemented with qualitative data.

8.6 Measures to Minimize Bias

Enrollment/Randomization/Masking Procedures

- There will be no randomization, as it is a convenience sample based on when learners have room in their schedule to rotate with the palliative care team

- Based on the way the intervention will be implemented, it is impossible to blind the educators or the rotators as to whether the rotators are in the control or intervention group
- The control and intervention survey data will not be analyzed until after all data is compiled (control data in August 2026 and intervention data in February 2027), and data will have all identifying information (timestamps, etc.) removed.
- Bias will be minimized in the qualitative data using triangulation – independent analysis by multiple personnel as well as comparison of open-ended survey data with focus group data

Section 9: Data Quality and Oversight

Survey data will be de-identified and collected via REDCap. It will be stored in their database until completion and publication of the study. It will be accessible only to authorized users via password. Data downloaded for analysis in an Excel file will have data and timestamps removed.

Focus group data will be de-identified when it is transcribed. It will be conducted over teleconference software (Teams) but recorded via audio recorders outside of the Teams software, so as to not capture visual data. Additionally, participant names will not be used, and they will be referred to as “participant 1”, “participant 2”, etc. Recording will be transcribed using Rev AI transcription software. Recordings and transcriptions will be stored on a password protected shared drive.

9.1 Study Team Quality Assurance and Quality Control

The highest risk for deviations in data quality is in the qualitative data, especially that which will be transcribed from the focus group. The Principal Investigator is responsible for maintaining quality control of the data.

9.2 Data Safety and Monitoring Plan

There is not an anticipated need for a Data Safety and Monitoring Plan considering the minimal risk of adverse events to subjects.

Section 10: Ethical Considerations

10.1 Ethical Standard

The study team will ensure that this study is conducted in full conformity with the Regulations for the Protection of Human Subjects of Research codified in 45 Part 46 of the Code of Federal Regulations, Children’s National Policies and Procedures and Good Clinical Practices.

10.2 Institutional Review Board (IRB)

The protocol, informed consent form(s), recruitment materials, and all participant materials will be submitted to the Children’s National IRB for review and

approval. Approval of both the protocol and the consent form will be obtained before any participant has given consent. Any change to the protocol, consent, recruitment materials and participant information sheets or letters will require IRB approval before implementation and use. The IRB will determine whether previously consented participants need to be re-consented

The IRB will be notified of study team updates via an amendment. Data Safety Monitoring Board (DSMB) Reports will not be submitted at the time of the continuing review or with another applicable IRB transaction due to the minimally risky nature of this study.

Other study events (e.g., protocol deviations, data monitoring reports) will be submitted per the Children's National IRB Reportable Events Module.

10.3 Maintaining Subject Privacy

Initial patient recruitment for the survey portion of the study will be done via email, and their data will be entered in Redcap. It is impossible to fully limit subject privacy during a focus group, so subjects will be informed in the information sheet that there is a risk of loss of privacy of the information they share in the focus group, as the researchers are not able to control the actions of the other participants. However, there will be an explicit expectation of respect for information shared with all participants, and the focus group will be conducted in a private virtual space.

10.4 Maintaining Study Data Confidentiality

Participant confidentiality is strictly held in trust by the participating investigators, their staff, the sponsor, and their agents. This confidentiality is extended to cover educational information relating to participants. Therefore, the study protocol, documentation, data, and all other information generated will be held in strict confidence. No information concerning the study or the data will be released to any unauthorized third party without prior written approval of the sponsor.

The sponsor's representatives and regulatory authorities (e.g., IRB, OHRP) may inspect all documents and records required to be maintained by the investigator. The clinical study site will permit access to such records.

The study participant's contact information will be securely stored at each study site for internal use during the study. At the end of the study, all research records will be stored in a secure location for the time period dictated by the sponsor and institutional regulations.

The research data will not include the participant's contact or identifying information. Rather, individual participants and their research data will be identified by a unique study identification number. The study data entry and study management systems used by research staff will be secured and password

protected. At the end of the study, all study databases will be archived at Children's National.

